# **6.2** Selection of Study Population

## **6.2.1** Main Patient Survey

The HAE patient survey study will target 300 or more persons with a self-reported diagnosis of HAE (type I, II, normal functioning C1-INH, and unknown) in the following countries: Argentina, Brazil, Colombia, Croatia, Denmark, Hungary, Ireland, Norway, Poland, Portugal, Romania, and Sweden. Approximately 10 to 120 participants will be targeted per country. As HAE prevalence is not available by country, target recruitment numbers will be based on country population (Table 1), in consultation with local experts and representatives of HAEi. Conservative estimates of HAE prevalence are 1 in 50,000 (Bygum, et al., 2012). The target numbers presented are based on consultation described above, and are not presented for the purpose of achieving any specified statistical power which would be needed for advanced statistical analyses.

Table 1. Target HAE patient survey recruitment by country

Country	Population*	Population with HAE*	Target Recruitment †
Argentina	45,195,774	904	40
Brazil	212,559,417	4,251	100
Colombia	50,882,891	1,018	50
Croatia	4,105,267	82	25
Denmark	5,792,202	116	10
Hungary	9,665,710	193	25
Ireland	4,937,786	99	10
Norway	5,421,241	108	10
Poland	37,846,611	757	40
Portugal	10,196,709	204	10
Romania	19,237,691	385	64
Sweden	10,099,265	202	10

\*Population numbers from worldometers.info. Population with HAE is estimated based on the best available prevalence data of 1 in 50,000. Proportion of Target Sample is determined by taking Targeted Recruitment and dividing by the desired minimum sample of 300.

† The numbers in this column were arrived at through consultation with HAEi, local KOLs, and local internal resources within Takeda. Further, we hope to achieve 500 participants, which is greater than the 394 total here. While we hope to achieve 500 participants, the 394 total presented here represents what we have been made to expect based on the above consultation.

# **6.2.2** Caregiver of a Pediatric Patient Survey

The Caregiver of a Pediatric Patient Survey study will target up to 250 caregivers of children and adolescents (≤ 17 years old) with a diagnosis of HAE (type I, II, normal functioning C1-INH, and unknown) in the following countries: Argentina, Brazil, Colombia, Croatia, Denmark, Hungary, Ireland, Norway, Poland, Portugal, Romania, and Sweden. If a caregiver of a pediatric patient is also an HAE patient themselves, they will be able to complete both the patient survey and the caregiver of a pediatric patient survey.

# **6.2.3** Caregiver of an Adult Patient Survey

The Caregiver of an Adult Patient Survey study will target up to 200 caregivers of adults (≥ 18 years old) with a diagnosis of HAE (type I, II, normal functioning C1-INH, and unknown) in the following countries: Argentina, Brazil, Colombia, Croatia, Denmark, Hungary, Ireland, Norway, Poland, Portugal, Romania, and Sweden. If a caregiver of an adult patient is also an HAE patient, they will be able to complete both the patient survey and the caregiver of an adult patient survey. Caregivers of adults will be recruited through adult participants who take the survey. The adult participant will be asked if they have a caregiver they would like to refer to the study, and be provided with a unique link to send to their caregiver. In this way, the responses of the adult patient and their caregiver can be compared.

# 6.2.4 Inclusion Criteria

To be eligible for the study, participants will be required to meet all of the following inclusion criteria:

# 6.2.4.1 HAE Patient Survey

- 1. Self-reported diagnosis of HAE (Types I, II, normal functioning C1-INH, or unknown type)
- 2. Age 18 years or older
- 3. Experienced at least 1 episode of angioedema or prodromal symptoms within the last year
- 4. Has been treated with a prescription medication for an angioedema attack within the last 2 years
- 5. Able to understand and provide consent
- 6. Willing to complete an web-based survey
- 7. Adequate fluency in the target language in which the survey is designed:

- o Spanish (Argentina & Colombia)
- o Brazilian Portuguese (Brazil)
- o Croatian (Croatia)
- o Danish (Denmark)
- Hungarian (Hungary)
- o English (Ireland)
- Norwegian (Norway)
- o Polish (Poland)
- o Portuguese (Portugal)
- o Romanian (Romania)
- o Swedish (Sweden)

# 6.2.4.2 Caregiver of a Pediatric Patient Survey

- 1. A primary caregiver of a child or adolescent who is aged 17 years or younger diagnosed with HAE (Types I, II, normal functioning C1-INH, or unknown type)
  - Primary caregiver means that the individual provides regular care or support on an unpaid voluntary basis. The individual is not a hired professional caregiver.
- 2. Age 18 years or older
- 3. Able to understand and provide consent
- 4. Willing to complete an web-based survey
- 5. Adequate fluency in the target language in which the survey is designed:
  - o Spanish (Argentina & Colombia)
  - o Brazilian Portuguese (Brazil)
  - o Croatian (Croatia)
  - Danish (Denmark)
  - Hungarian (Hungary)
  - o English (Ireland)
  - Norwegian (Norway)
  - o Polish (Poland)
  - o Portuguese (Portugal)
  - o Romanian (Romania)
  - Swedish (Sweden)

# 6.2.4.3 Caregiver of an Adult Patient Survey

- 1. A caregiver of an adult who is aged 18 years or older diagnosed with HAE (Types I, II, normal functioning C1-INH, or unknown type)
  - Caregiver means that the individual provides regular care or support on an unpaid voluntary basis. The individual is not a hired professional caregiver.

- 2. Age 18 years or older
- 3. Able to understand and provide consent
- 4. Willing to complete an web-based survey
- 5. Adequate fluency in the target language in which the survey is designed:
  - Spanish (Argentina & Colombia)
  - o Brazilian Portuguese (Brazil)
  - o Croatian (Croatia)
  - o Danish (Denmark)
  - Hungarian (Hungary)
  - o English (Ireland)
  - o Norwegian (Norway)
  - o Polish (Poland)
  - o Portuguese (Portugal)
  - o Romanian (Romania)
  - Swedish (Sweden)

#### 6.2.5 Exclusion Criteria

There are no exclusion criteria

#### 6.3 Data Source/Data Collection Process

The source of information for the study will be self-reported data collected from web-based surveys completed by adult HAE patients and caregivers. Participants are members of or referred by patient advocacy organizations, medical societies, or healthcare providers in the target countries.

# 6.3.1 Enrolment Data

Eligibility and screening data for this study will be retrieved from the web-based screeners presented at the beginning of the patient and caregiver surveys.

# 6.3.2 Survey Data

Each survey will be administered through an online portal (Confirmit). Localities will be well served with a general, web-based survey hosting on secure servers.

## **6.3.2.1** HAE Patient Survey

Patient-reported data will be collected via a web-based survey that includes questions on patient clinical characteristics, demographic characteristics, humanistic burden of illness, and economic burden of illness. The survey incorporates validated patient-reported outcome questionnaires in addition to questions focused on ascertaining HAE disease status, frequency of attacks, HAE treatment management, and health care resource utilization. The HAE Patient Survey is organized by the following sections:

- 1. HAE History and Current Treatment
- 2. Most Recent Attack Symptoms and Treatment
- 3. Patient-Reported Outcomes Instrument (please see the details in section 6.4.3)
  - a. Angioedema Control Test (AECT)
  - b. Angioedema Quality of Life Questionnaire (AE-QoL)
  - c. Work Productivity and Activity Impairment Questionnaire: General Health (WPAI-GH)
  - d. 12-Item Short Form (SF-12 v2.0)
  - e. Hospital Anxiety and Depression Scale (HADS)
- 4. Health Care Resource Utilization
- 5. General Health & Socio-demographic Information
- 6. Additional Questions

# **6.3.2.2** Caregiver of a Pediatric Patient Survey

Data in the Caregiver of a Pediatric Patient Survey will be collected via a web-based survey that includes questions on patient clinical characteristics, humanistic burden of illness on pediatric patients, caregiver impacts, and economic burden of illness. The survey also includes questions focused on ascertaining the pediatric patient's HAE disease status, frequency of attacks, HAE treatment management, and questions related to use of androgens. The Caregiver of a Pediatric Patient Survey is organized by the following sections:

- 1. Patient Information
- 2. Patient's Most Recent Angioedema Attack
- 3. Impacts of HAE on Child/Adolescent Patient
- 4. Caregiving Information
- 5. Caregiver Impacts
- 6. Background & Socio-demographic Information

# 6.3.2.3 Caregiver of an Adult Patient Survey

Data in the Caregiver of an Adult Patient Survey will be collected via a web-based survey that includes questions on demographic characteristics, patient clinical characteristics,

caregiver impacts, and economic burden of illness. The patient survey is organized by the following sections:

- 1. Patient Information
- 2. Caregiving Information
- 3. Impacts on Caregiver
- 4. Background and Socio-demographic information

# **6.3.3** Patient-Reported Outcome Questionnaires

The patient survey will include patient-reported outcome questionnaires described in sections 6.4.3.1-6.4.3.5.

# **6.3.3.1** Angioedema Control Test (AECT)

The AECT (Weller, et al., 2019) is a questionnaire used to determine the level of disease control in patients with angioedema (Weller, 2019). It consists of four questions with five answer options each. The four questions of the AECT address the frequency of signs and symptoms of the disease (question 1), quality of life impairment (question 2), mental health (question 3), and efficacy of treatment (question 4). Each answer option is awarded 0 to 4 points, from no control (0 points) to complete control (4 points). Thus, a maximum of 4 points per question/answer and a total maximum of 16 points (complete control) can be achieved. The more points patients score, the better their control of the disease. An AECT score of 10 or greater indicates controlled disease. Values of 9 and lower reflect poor control and a need for better treatment (Weller, et al., 2020).

# 6.3.3.2 Angioedema Quality-of-Life Questionnaire (AE-QoL)

The AE-QoL, a patient-reported questionnaire, was developed to assess quality of life impairments in patients with recurrent angioedema (Weller, et al., 2016). It consists of 17 items regarding the extent to which angioedema has affected the patient's daily life over the last 4 weeks. The measure is self-administered and consists of four dimensions (functioning, fatigue/mood, fears/shame, and nutrition). Table 2 shows the items associated with each scale score, with higher scores indicating increased severity. The AE-QoL is meant to be evaluated

by using its four individual dimensions (profile instrument) but can also be used to determine a total score (index instrument):

The AE-QoL dimension scores as well as the AE-QoL total score are calculated by using the following formula:

(Σ items - min Σ items / max Σ items - min Σ items) x 100

## Example:

Dimension "Functioning":

Item 1: answer 3

Item 2: answer 2

Item 3: answer 4

Item 4: answer 5

 $\Sigma$  items: (3+2+4+5) = 14

min  $\Sigma$  items: (1+1+1+1) = 4

max  $\Sigma$  items: (5+5+5+5) = 20

Enter values in formula:  $(14 - 4 / 20 - 4) \times 100 = 62.5\%$ 

The AE-QoL dimension scores correspond to the mean of the items within each dimension. If some items are missing, the total of the items within the dimension is divided by the number of the non-missing items. The same holds for the AE-QoL total score. An AE-QoL dimension score should not be calculated if more than one item is missing in that dimension. The AE-QoL total score should not be calculated if more than 25% of items (>4 items) are missing. Please note that only calculating the raw dimension scores (mean of the item scores within each scale) and the raw total score (mean of all item scores) would be easier than the above described procedure. However, in case of missing answers, an inter-individual as well as an intra-individual comparison of AE-QoL results would be limited. The above described linear transformation of all raw scores into percentage scores (indicating the location of the raw scores in relation (in percent) to its maximum possible score) solves this problem and makes it possible to judge and compare AE-QoL results even when single items are missing. The linear transformation of raw scores results in minimal and highest possible scale and total scores of 0 and 100, respectively.

Table 2. Scoring the AE-QoL

Dimensions and Total Score	Number of Items	Score Range	Item Numbers
Functioning	4	4 to 20	1, 2, 3, 4
Fatigue/Mood	5	5 to 25	6, 7, 8, 9, 10
Fears/Shame	6	6 to 30	12, 13, 14, 15, 16, 17
Nutrition	2	2 to 10	5, 11
Total score	17	17 to 85	1 to 17

# 6.3.3.3 Work Productivity and Activity Impairment Questionnaire – General Health (WPAI-GH)

The Work Productivity and Activity Impairment—General Health (WPAI–GH) is a self-administered questionnaire (Reilly et al., 1993) comprising six questions that measure the effect of health problems on participants' ability to work and participate in regular activities based on their experiences in the previous 7 days. The WPAI–GH includes four domains (absenteeism, presenteeism, work productivity loss, and activity impairment). All participants are asked whether they are employed (Q1) and about the degree their health problems affect regular activities (Q6). Employed participants are asked about hours of work missed due to health problems (Q2), hours of work missed due to other reasons (Q3), hours actually worked (Q4), and the degree health problems affected their productivity while working (Q5).

Responses to the items are scored to produce the following four domains:

- Absenteeism: work time missed due to health problems = Q2/(Q2+Q4)
- Presenteeism: impairment while working due to health problems = Q5/10
- Work Productivity Loss: overall work impairment due to health problems = Q2/(Q2+Q4)+[(1-Q2/(Q2+Q4))x(Q5/10)]
- Activity Impairment: activity impairment due to health problems = Q6/10

Each score is then multiplied by 100 to express domains in terms of impairment percentages, with higher numbers indicating greater impairment and less productivity (i.e., worse outcomes). If an item contributing towards a score is missing, the score will not be calculated.

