# 2 Introduction

Hereditary angioedema (HAE) is a rare genetic disorder characterized by recurrent episodes of edema in the face, extremities, trunk, abdomen, genitals, and upper respiratory tract (Bygum et al., 2012; Betschel et al., 2014). Angioedema attacks can be random or occur as the result of trauma. The frequency and duration of attacks can vary. Untreated patients experience attacks every one to two weeks on average, with most episodes lasting three to four days (Bygum et al., 2012, Genetics Home Reference, 2017). HAE is estimated to affect 1 in every 50,000 in the general population (Bygum et al., 2012). Symptoms usually begin in childhood and worsen during puberty; however, 6.1-13.7% of patients may be asymptomatic or have delayed symptom onset (Bygum et al., 2012). The rarity and lack of awareness of the condition often result in delayed diagnosis (Bygum et al., 2012).

HAE is caused by C1 inhibitor deficiency and is categorized into three types depending on the level and function of the C1 inhibitor. HAE Type I is the most common form, representing approximately 85% of cases, and is caused by low antigenic and functional levels of C1 inhibitor. HAE Type II accounts for approximately the remaining 15% of cases and is associated with a normal C1 inhibitor protein level, but impaired function of the protein. The third type of HAE is associated with normal C1 inhibitor function (HAE-nC10INH) and is rare; it's true prevalence and exact pathogenesis are unknown (Betschel et al., 2014; Genetics Home Reference, 2017).

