## 6.6.5 Participant Completion of the Study

Participants should be included in the study only once. Data erroneously collected from participants without electronic consent will not be included in or will be deleted from the database.

A survey is considered completed if the participant answered all required questions. The survey will not progress unless a response is provided to a required question. Upon completion of the survey, the participant will be provided with a unique completion code. The participant will email the completion code to their country-specific patient advocacy, professional organization, medical society, or healthcare provider (Ireland and Portugal), which will then confirm the code with ICON. Upon confirmation, the patient advocacy organization, medical society, or healthcare providers will remunerate participants for the completion of the survey, per the following:

- HAE Patient Survey: An equivalent of \$45 USD
- Caregiver of a Pediatric Patient Survey
  - o First completion: An equivalent of \$30 USD
  - Subsequent completions: An equivalent of \$15 USD
- Caregiver of an Adult Patient Survey: An equivalent of \$30 USD

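### The WPAI-GH scoring rule makes no exception for employed patients who worked zero hours: an unanswered Q5 discards a work productivity loss score already fixed at 100%, and a forced Q5 contaminates presenteeism

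*Protocol*

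**What the plan says.** Section 6.3.3.3 of the protocol describes six questions, answered "based on their experiences in the previous 7 days". Employed respondents report hours missed through ill health (Q2), hours missed for other reasons (Q3), hours worked (Q4), and an impairment rating (Q5) for "the degree health problems affected their productivity while working (Q5"). Four scores follow, each multiplied by 100:

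- absenteeism, A = Q2/(Q2+Q4);
- presenteeism, Q5/10;
- work productivity loss, A + (1 - A) x Q5/10;
- activity impairment, Q6/10.

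The section closes with the missing-item rule: "If an item contributing towards a score is missing, the score will not be calculated". It has no separate provision for zero hours worked and mentions no skip of Q5 in that case.

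Three other places bear on this. Section 6.6.5 says of the web survey: "The survey will not progress unless a response is provided to a required question". Section 9.5 expects no missing data before completion or break-off, refers scoring and missing items to the developers' guidelines, and rules out imputation. WPAI-GH is named in patient Objective 3 (sections 3.1.1 and 9.1.1), and its scores are dependent variables under Secondary Objective 2 (section 9.1.4).

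**The concern.** Q5 is a contributing item of work productivity loss, so the rule makes that score depend on it. A person who worked no hours cannot rate impairment while working. That is also the one situation in which the formula does not need Q5. If the item is empty, the rule removes a value that is already determined, and every value removed in this way is 100%. The loss depends on the outcome itself and can only pull the mean down. The same person would still count as 100% in absenteeism, so the two domains would be averaged over different people without the tables showing it.

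If the survey instead insists on an answer to Q5, work productivity loss comes out correctly, but an answer with no meaning goes into presenteeism.

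A third case is an employed person absent all week for other reasons only (Q2 = Q4 = 0). Every item may be answered, so the missing-item rule is not triggered, yet the ratio is 0/0.

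**Working it through.** The protocol gives no numerical result on this point, so there is no figure to reproduce.

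**1. The formula at zero hours worked.** With Q4 = 0 and Q2 > 0, A = Q2/(Q2+0) = 1. Work productivity loss is then 100 x [1 + (1 - 1) x Q5/10] = 100 for any Q5. Evaluated at Q2 = 8, 20 and 40 hours with every Q5 from 0 to 10, the result is 100 each time.

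**2. Contrast with Q4 > 0.** At Q2 = Q4 = 20 the score is 50, 75 and 100 for Q5 = 0, 5 and 10. At Q2 = 39, Q4 = 1 it runs from 97.5 to 100. Q5 is needed once any hours are worked, and only then.

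**3. Q2 = Q4 = 0.** Absenteeism and work productivity loss are both 0/0 and undefined.

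**4. Effect on each score when Q4 = 0 and Q2 > 0:**

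| Score | Q5 blank or skipped | Q5 forced |
|---|---|---|
| Absenteeism | 100% | 100% |
| Work productivity loss | discarded, though fixed at 100% | 100% |
| Presenteeism | not calculated, as it should be | includes a meaningless answer |
| Activity impairment | unaffected | unaffected |

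**5. Size if Q5 is blank.** Let f be the share of such patients among employed respondents with Q2 + Q4 > 0, and m the mean work productivity loss of the others. The mean with them is (1 - f) x m + f x 100; without them it is m. The shortfall is f x (100 - m). Both f and m are assumptions:

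| f | m = 20 | m = 30 | m = 40 |
|---|---|---|---|
| 1% | 0.8 | 0.7 | 0.6 |
| 2% | 1.6 | 1.4 | 1.2 |
| 5% | 4.0 | 3.5 | 3.0 |

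For head counts, take 300 patients (the minimum in section 9.3) to 394 (the total of the country targets in Table 1), with an assumed 50-70% employed. Then f = 2% is about 300 x 0.5 x 0.02 = 3 to 394 x 0.7 x 0.02 = 5.5 people, and f = 5% is about 7.5 to 13.8.

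**6. Size if Q5 is forced.** Let g be the share of employed respondents with zero hours worked for any reason, p the presenteeism mean of those who worked, and q the mean of the meaningless answers, on the 0-100 scale. The presenteeism mean shifts by g x (q - p). Assuming g = 5% and p = 20-40, the extremes are 0.05 x (0 - 40) = -2 and 0.05 x (100 - 20) = +4 points. The direction is unknown.

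**The case against.** The strongest reply is that nothing shows Q5 will be empty. Section 6.3.3.3 has employed respondents answer it and states no skip. Section 6.6.5 blocks progress past required questions, and section 9.5 expects no missing items. On that reading nobody is lost from work productivity loss. This stands: a reader might infer that the rule does delete the worst-affected workers, and the protocol does not establish it. The survey in Appendix C, which would settle whether Q5 is required, skipped or optional at Q4 = 0, is not in the text at hand. The reply does not clear the scoring, however, because forcing Q5 moves the fault into presenteeism and leaves 0/0 open.

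A second reply is that section 9.5 defers to the developers' guidelines and that zero-denominator handling belongs in the analysis plan. The content of those guidelines is not in the protocol, and a general reference does not withdraw a specific rule stated for this instrument. Silence on 0/0 alone would be ordinary programming detail; a written rule that discards a determined score is more than that. Nor does the ban on imputation apply, since 100% follows from the answers given.

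A third reply concerns size. The shares are assumed, and the protocol describes attacks in untreated patients "with most episodes lasting three to four days", so a wholly missed week within one 7-day window may be uncommon. The study is descriptive and one of four domain scores is at issue. All of this stands and limits the severity.

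**Conclusion.** The point holds conditionally. As written, the scoring goes wrong for employed patients with Q4 = 0 and Q2 > 0 under either survey design: work productivity loss is discarded if Q5 is empty, or presenteeism is contaminated if Q5 is forced. The algebra is exact. The size is not known: f = 2-5% and m = 20-40 give a shortfall of about 1.2 to 4 points in mean work productivity loss, resting wholly on those assumptions and on Q5 being empty.

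Two stronger readings are not supported. One is that these patients drop out of WPAI-GH altogether; absenteeism and activity impairment are still scored. The other is that the gradient across attack-frequency groups is flattened. That would follow if Q5 were empty and wholly missed weeks clustered among patients with many attacks, which is plausible, but the protocol gives no figure for it.

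Severity is moderate to minor: the outcome is named in Objective 3 and Secondary Objective 2, but the number affected is unknown and could be zero.

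**What to change.** Amend the scoring paragraph in section 6.3.3.3 to state that:

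- when Q4 = 0 and Q2 > 0, absenteeism is 100%, work productivity loss is 100% without reference to Q5, and presenteeism is not applicable;
- when Q2 + Q4 = 0, absenteeism and work productivity loss are missing and presenteeism is not applicable;
- the missing-item rule applies in all other cases;
- the number of respondents contributing to each domain is reported beside its summary.

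If the survey can still be changed, skip Q5 when Q4 = 0. If it is already in the field, the scoring statement alone is enough: it keeps the work productivity loss scores and removes meaningless Q5 answers from presenteeism. The cost is a few lines of scoring text, one table row for denominators and, at most, one skip instruction.
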